7. SUMMARY OF STUDY POPULATION DATA

7.1. Subject Disposition

The disposition of all subjects who are enrolled in Period 1 will be presented in a table. The disposition summary will include the number and percentage of subjects in FAS Period 1, PPS Period 1, Safety Population Period 1, completers and non-completers at Month 12 Visit. In addition, Sjögren Patients in Period 1, Subjects Markedly Improved in Period 1 will also be presented.

In addition, the subject enrollment will be summarized by geographic region, country, and site.

Subject disposition of Period 2 will be presented in a separate table in terms of all subjects who are randomized in Period 2 by treatment and overall. The summary will include the number of subjects in the FAS Period 2, PPS Period 2, Sjögren Patients in Period 2, and Safety Population Period 2 as well as completers and non-completers at Month 36 Visit along with the primary discontinuation reason.

The subject distribution of randomized subjects in Period 2 will also be summarized by geographic region, country, and site.

7.2. Demographics and Other Baseline Characteristics

For Period 1 summary, subject demographics and baseline characteristics will be summarized for the FAS Period 1 population, the Sjögren Patients Population, and the Markedly Improved Subjects in Period 1. The descriptive summary will be repeated for the FAS Period 2 population for each treatment group and overall for Period 2 summary and Sjögren Patients to satisfy FAS Period 2. The Entire Study summary will not be provided because the FAS Entire Study population is same as the FAS Period 2 population.

For subject demographics, the following variables will be summarized:

- Age at enrollment (continuous and categorical: < 65 years or ≥ 65 years)
- Sex (categorical: male or female)
- Ethnicity (categorical: Hispanic/Latino or Not)
- Race (categorical: American Indian or Alaska Native, Asian, Black or African American, Native Hawaiian or Other Pacific Islander, White, or Other)

For baseline characteristics, the following variables will be summarized for study eye (summarize for fellow eye if needed):

- CFS Score on the Modified Oxford Scale (<3 and each category)
- Schirmer test without anaesthesia (<10 mm/5 min or ≥10 mm/5 min)
- Symptom Score (Number of subjects with a score ≥ 2)
- Primary diagnosis (dry eye disease: both eyes or single eye)
- Duration of dry eye disease (years)

- Sjögren Disease status (yes or no) where appropriate
- Alcohol use [yes or no; if yes, ≤ 30 g per day (women) or ≤ 40 g per day (men), > 30 g per day (women) or > 40 g per day (men)]
- Illicit or recreational drug use (yes or no)
- Tobacco use
 - o Yes
 - Ex-smoker (number of packets per year and duration of smoking)
 - Current smoker (number of packets per year and duration of smoking)
 - o No
- Passive tobacco use (yes, no)

7.3. Medical History

For this study, medical and surgical history and adverse events will be coded using MedDRA 23.1. Each medical event will be classified into a SOC and mapped to a Preferred Term (PT).

The medical and surgical history will be summarized for the FAS Period 1 population, the Sjögren patients population, and the subjects markedly improved in Period 1. Subjects reporting any medical and surgical history at baseline will be tabulated by SOC and PT for each planned treatment and overall. These will be also summarized for the FAS Period 2 population and Sjögren Patients to satisfy FAS Period 2.

7.4. Protocol Deviations

In this study, protocol deviations are categorized as follows:

- Informed consent
- Inclusion/exclusion criteria
- Concomitant treatment
- Investigational product
- Procedures/tests/assessments
- Protocol Implementation
- Randomization
- Safety reporting
- Time Window
- Other

A protocol deviation is considered important if it may affect the subject's rights, safety, or well-being and/or the completeness, accuracy, and reliability of the study data. Santen's study team will review all protocol deviations and determine the list of important protocol deviations prior to database lock.

The protocol deviations will be summarized for Period 1 and Period 2 separately using the FAS Period 1 subjects and the FAS Period 2 respectively. Subjects with any important protocol deviations will be tabulated by deviation category by study period and for each planned treatment and overall for Period 2. In addition, important protocol deviations will also be listed.

7.5. Prior and Concomitant Medications

Non-study medications will be categorized into prior medications and concomitant medications. Specifically, the *prior medication* is defined as any non-study medication taken and ended prior to the treatment start date. The *concomitant medication* is defined as any non-study medication taken concurrently while on the study medication, i.e., the treatment period of a concomitant medication taken by a subject needs to overlap with his/her treatment period of the study medication.

For this study, non-study medications, including prior and concomitant medications, will be coded using WHO Drug, Version Enhanced (September 2019) format B3. Each non-study medication will be classified using the Anatomical-Therapeutic-Chemical (ATC) classification system and mapped to a WHO Drug preferred drug name.

Non-study medications will be summarized for the Safety population. Prior medications will be summarized for both the Safety Population Period 1 and Period 2. Concomitant medications will be summarized by study period. For Period 2, concomitant medications will be summarized by each actual treatment received and overall. A subject will be counted at most once for each medication per period, even if the subject took the same medication on multiple occasions. In addition, prior medications and concomitant medications will also be listed, separately.

For the Sjögren patients population, prior and concomitant medication uses will be summarised separately.

7.6. Treatment Compliance

Compliance to the study medication use is tracked on the Compliance eCRF as the number of single dose medication containers not used and returned.

Due to the irregularities in returning containers caused by COVID-19 situation, the treatment compliance will be assessed by study period rather than by intervals based on scheduled visits as specified in the protocol. Since some visits, for example, happened remotely, dispensing or returning of study drug could not happen on a scheduled time. Compliance rate will be calculated for Period 1, and Period 2, respectively.

For a given analysis period, compliance rate will be calculated using the following formula, which assumes that the unreturned containers are not used:

Treatment Compliance Rate (%) in Period x

 $= \frac{\text{No. of dispensed containers-(No. of returned unused containers + No. of unreturned containers)}}{\text{Duration of Period x}} \times 100$

where the Duration of Period x is the number of days subjects should have administered study medication in the analysis period, calculated as

Duration of Period x =end date of study drug in Period x -start date of study drug in Period x.

Compliance rate of \geq 80% will be treated as compliant. Compliance will be summarized continuously and categorically (compliant and non-compliant) for FAS subjects for Period 1 and Period 2 separately. Period 2 summaries will be performed by planned treatment and overall.

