# **8.3.** Treatment Compliance

Patient compliance will be assessed at each visit by investigator by questioning the patient and comparison to drug accountablity. All reported incidents of the lack of compliance will be recorded on the eCRF with the reasons. If a patient is persistently noncompliant with the study medication, the patient should be withdrawn from the study. All patients should be reinstructed about the dosing requirement during study visits. The authorized study personnel conducting the re-education must document the process in the patient source records.

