7.7. Exposure to Study Medication

The *extent of exposure* to study medication will be assessed by duration of treatment exposure, derived as:

Duration of treatment exposure = Treatment end date - Treatment start date + 1 Specially,

Period	Treatment Start Date	Treatment End Date
Period 1	Period 1 treatment start date	Period 1 treatment end date
Period 2	Period 2 treatment start date	Period 2 treatment end date
Entire Study Period (for subjects who entered Period 2 and received IKERVIS treatment only)	Period 1 treatment start date	Period 2 treatment end date

For subjects in the Safety Population, the duration of exposure will be summarized using descriptive statistics continuously and categorically for Period 1, Period 2 (by actual treatment received and overall), and for the entire study (for subjects who entered Period 2 and received treatment (IKERVIS/IKERVIS or IKERVIS/Vehicle) or for subjects who received IKERVIS treatment during Period 1 or 2) separately.

The duration of exposure categories are:

- Period 1: 1-90, 91-180, 181-270, or \geq 271 days
- Period 2: 1-90, 91-180, 181-270, 271-360, 361-450, 451-540, 541-630, \geq 631days
- Entire study period: 1-90, 91-180, 181-270, 271-360, 361-450, 451-540, 541-630, 631-720, 721-810, 811-900, 901-990, or \geq 991 days

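### SAP 7.6 scores every container not returned as a missed dose, so lost packaging can class an adherent patient as non-compliant; separately, its denominator is one day short

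*SAP*

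**What the plan says.** SAP 7.6 (Treatment Compliance) bases compliance on container counts. It states that "compliance rate will be calculated using the following formula, which assumes that the unreturned containers are not used", and gives the numerator as "No. of dispensed containers-(No. of returned unused containers + No. of unreturned containers").

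The denominator is described in words as "the number of days subjects should have administered study medication in the analysis period", but the formula given for it is "Duration of Period x =end date of study drug in Period x -start date of study drug in Period x". For exposure, SAP 7.7 works from period start and end dates and writes "Duration of treatment exposure = Treatment end date - Treatment start date + 1"; SAP 4.1.5 also adds the 1.

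A rate at or above the cut-off counts as compliant ("80% will be treated as compliant"). The rate and the two-way category are summarised for the full analysis set, separately for Period 1 and Period 2. The section explains why it works by whole period and not by visit interval: "Due to the irregularities in returning containers caused by COVID-19 situation". It adds that some visits were remote, so drug could not be dispensed or returned on schedule.

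Protocol 9.6 tells patients to keep both used and unused containers and bring them to each visit. Protocol 8.3 has the investigator question the patient and compare the answer with drug accountability, and says "All reported incidents of the lack of compliance will be recorded on the eCRF with the reasons".

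**The concern.** Both used and unused containers are meant to come back. Dispensed minus returned-unused minus unreturned therefore leaves only the used containers physically handed in. A container that was used and then lost, thrown away or never collected scores the same as a skipped dose. The section itself gives a logistical reason for irregular returns, yet the formula reads every non-return as non-adherence and reports no alternative figure.

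At stake is whether the compliance table can be trusted. A primary objective is the long-term efficacy of continuous treatment, and SAP 8.2.1 estimates IKERVIS-vehicle differences in Period 2. A reader weighing those results will look at adherence. A single figure that mixes missed doses with missing packaging, then split at 80%, does not show which of the two is being seen.

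The denominator is a second and independent matter: the formula does not compute what the sentence before it describes.

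**Working it through.** The documents state no computed compliance figure, so there is none to reproduce. The check applies the SAP 7.6 formula to a patient who uses one container every night.

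**Inputs**
- One dose nightly (Protocol 9.5); one container treats both eyes (Protocol 9.2). This gives one container per day.
- Period 1 starts on Day 1 and ends the day before the Month 12 visit (SAP 4.1.2). With the visit on Day 360 the end is Day 359, so there are 359 doses.
- SAP denominator: 359 − 1 = 358.
- Assumption: one 110-container box at each of the four Period 1 dispensings, 440 in all. Protocol 9.2 gives the box size but states one box per visit only for Period 2. The number dispensed cancels out of the rate.

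**Period 1, everything returned**
- Returned unused: 440 − 359 = 81.
- Rate: (440 − 81)/358 = 359/358 = 100.3%. With the extra day: 359/359 = 100.0%.

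**Period 1, one 90-day quarter never returned**
- Unreturned: 110. Returned unused from the other three boxes: 81 − 20 = 61.
- Rate: (440 − 61 − 110)/358 = 269/358 = 75.1%. If the 20 spares come back and only the 90 empties are lost, the numerator is the same: 440 − 81 − 90 = 269.
- If the lost box is the first (89 nights): 270/358 = 75.4%.
- With the extra day: 269/359 = 74.9%. Correcting the denominator lowers the rate and leaves the category unchanged.

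**Break-even at nominal visits**
- 80% of 358 is 286.4, and 359 − 286.4 = 72.6.
- 72 lost empties: 287/358 = 80.2%, compliant. 73 lost empties: 286/358 = 79.9%, non-compliant.

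**Visit windows**
- Each of the four visits can fall on any of 15 days (±7), giving 15⁴ = 50,625 schedules. With four choices of lost quarter there are 202,500 cases.
- The rate runs from 70.7% (visits on Days 83, 173, 277 and 353, third quarter lost: (352 − 104)/351 = 248/351) to 79.5% (Days 97, 187, 263 and 367, third quarter lost: (366 − 76)/365 = 290/365). No case reaches 80%.

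**Period 2** (Day 360 to Day 1079: 720 doses, SAP denominator 719)
- One lost quarter: (720 − 90)/719 = 630/719 = 87.6%, compliant.
- Two lost quarters: (720 − 180)/719 = 540/719 = 75.1%, non-compliant.

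**Opposite bound, Period 1, one quarter lost**
- Counting all unreturned containers as used, uncapped: (440 − 61)/359 = 379/359 = 105.6%.
- Capped at one per day, the lost box contributes 90: (269 + 90)/359 = 100.0%.
- The defensible statement for this patient is a range of 74.9% to 100%; the SAP reports only its bottom end.

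**The case against.** The strongest reply is that the convention is openly stated and conservative, and that the opposite assumption would overstate adherence. The move to whole-period counting is also a real mitigation: containers handed in at a later visit in the same period are fully credited, and that patient scores 100.3%. Irregular timing means delay more often than permanent loss, and neither document says how often containers never came back. Period 1 is single-arm with no testing. In Period 2, where the arms are compared, one lost quarter still passes. No specified analysis uses the 80% category.

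Most of this stands, and it limits the point. It does not answer it: whole-period counting does nothing for containers that never return, and a lower bound shown as the only estimate, then dichotomised, is not labelled as a bound.

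Stronger readings that a reader might infer, and that the documents do not support:
- *The short denominator causes the misclassification.* It works the other way, raising the rate by 0.2 to 0.3 points.
- *The 80% category decides who is in the PPS.* SAP 6 requires the protocol to be fulfilled on interventions but cites no compliance threshold; under SAP 7.4 the study team determines important deviations by review.
- *Recorded missed doses could replace the container count.* Protocol 8.3 records reported incidents with reasons, not a dose count.
- *Unreturned open-label drug was used in the vehicle arm.* Nothing in the documents shows this, and used and unused containers are due for collection at every Period 1 return visit.

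**Conclusion.** The point holds as two separate errors in SAP 7.6. First, counting every unreturned container as unused misclassifies a fully adherent Period 1 patient whose containers for one quarter are never returned within the period. The rate is 75.1% at nominal visits and below 80% on every in-window schedule; Period 2 needs two lost quarters. Second, the denominator is one day short of its own description and of the inclusive count elsewhere in the SAP, so perfect adherence exceeds 100%.

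The figures assume one container per night, full adherence, and permanent non-return within the period. How many patients are affected cannot be derived from the documents. The certain consequence is a misleading descriptive compliance rate and category. An effect on the PPS would arise only if compliance were used to define that set.

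**What to change.** In SAP 7.6:
1. Use end date minus start date plus 1 as the denominator.
2. Report the rate and the 80% category under both bounds: unreturned counted as unused, and unreturned counted as used with a cap of one container per day. Label the present formula as the lower bound.
3. If compliance is used to define the PPS, state that no patient is excluded on container non-return alone.

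The cost is a few lines of SAP text and some extra table rows. The counts needed (dispensed, returned unused, unreturned) are already inputs to the present formula. The downside is that compliance appears as a range and not as one figure.

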7.7. Exposure to Study Medication

The *extent of exposure* to study medication will be assessed by duration of treatment exposure, derived as:

Duration of treatment exposure = Treatment end date - Treatment start date + 1 Specially,

Period	Treatment Start Date	Treatment End Date
Period 1	Period 1 treatment start date	Period 1 treatment end date
Period 2	Period 2 treatment start date	Period 2 treatment end date
Entire Study Period (for subjects who entered Period 2 and received IKERVIS treatment only)	Period 1 treatment start date	Period 2 treatment end date

For subjects in the Safety Population, the duration of exposure will be summarized using descriptive statistics continuously and categorically for Period 1, Period 2 (by actual treatment received and overall), and for the entire study (for subjects who entered Period 2 and received treatment (IKERVIS/IKERVIS or IKERVIS/Vehicle) or for subjects who received IKERVIS treatment during Period 1 or 2) separately.

The duration of exposure categories are:

- Period 1: 1-90, 91-180, 181-270, or \geq 271 days
- Period 2: 1-90, 91-180, 181-270, 271-360, 361-450, 451-540, 541-630, \geq 631days
- Entire study period: 1-90, 91-180, 181-270, 271-360, 361-450, 451-540, 541-630, 631-720, 721-810, 811-900, 901-990, or \geq 991 days

8. EFFICACY ANALYSES

Unless otherwise specified, all efficacy analyses will be performed on the study eyes of the FAS Period 1 population, the Sjögren Patients in Period 1, the Subjects Markedly Improved in Period 1, the FAS Period 2 population, the FAS Entire Study population, and Sjögren Patients to satisfy FAS Period 2 (or FAS Entire Study Population).

8.1. Analysis of Primary Efficacy Endpoint

The primary efficacy endpoint is the correlation between change from baseline in CFS score and SANDE symptoms score at each visit, and cross correlation of sign at visit X versus symptoms at visit X+i, if any. Missing data will not be imputed.

[figure not shown]

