### 4.1.1. Clinical Experience

The approval by the European Commission of IKERVIS® for the treatment of severe keratitis in DED patients was mainly based on the efficacy and safety of results of two randomised, double-masked, vehicle-controlled clinical studies in adult patients with dry eye disease (keratoconjunctivitis sicca).

In the 12 month, double-masked, vehicle controlled, pivotal clinical trial (NVG10E117/SANSIKA study - Leonardi 2016), 246 Dry Eye Disease (DED) patients with severe keratitis [defined as a corneal fluorescein staining (CFS) score of 4 on the modified Oxford scale] were randomised to one drop of IKERVIS® or vehicle daily at bedtime for 6 months. Patients randomised to the vehicle group were switched to IKERVIS® after 6 months. The primary endpoint was the proportion of patients achieving by Month 6 at least a two-grade improvement in keratitis (CFS) and a 30% improvement in symptoms, measured with the Ocular Surface Disease Index (OSDI). The proportion of responders in the IKERVIS® group was 28.6%, compared to 23.1% in the vehicle group. The difference was not statistically significant (p=0.326).

The severity of keratitis, assessed using CFS, improved significantly from baseline at Month 6 with IKERVIS® compared to vehicle (adjusted mean change from baseline was -1.764 with IKERVIS® vs. -1.418 with vehicle, p=0.037). The proportion of IKERVIS®-treated patients with at least a 3-grade improvement in CFS score at Month 6 (from 4 to 1, 0.5 or 0) was 35.6%, compared to 14.4% of vehicle-treated patients (p=0.001, post-hoc analysis). The beneficial effect on keratitis was maintained in the open phase of the study, from Month 6 and up to Month 12.

The mean change from baseline in the 100-point OSDI score was -13.6 with IKERVIS® and -14.1 with vehicle at Month 6 (p=0.858). In addition, no improvement was observed for IKERVIS® compared to vehicle at Month 6 for other secondary endpoints, including ocular discomfort score, Schirmer test, use of concomitant artificial tears, investigator's global

evaluation of efficacy, tear break-up time, lissamine green staining, quality of life score, and tear osmolarity.

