### 4.2. Rationale for the Proposed Study

The approval by the European Commission of IKERVIS® for the treatment of severe keratitis in DED patients was mainly based on the efficacy and safety of results of two randomised, double-masked, vehicle-controlled clinical studies following over 6 months and 12 months (SICCANOVE and SANSIKA, respectively) in adult patients with dry eye disease (keratoconjunctivitis sicca). However, these studies did not demonstrate a beneficial effect of IKERVIS® compared to Vehicle on symptoms. The CHMP acknowledged the difficulty to reach both endpoints (ie. significant effect on both signs and symptoms) as the symptoms of DED patients with severe keratitis usually correlate poorly with the objective clinical findings such as epithelial defects visible with fluorescein staining (Baudouin 2014).

In DED patients with severe keratitis, a positive effect of a medication on symptoms may be impaired by the high degree of ocular surface damage which may reduce the corneal sensation. Additionally, there might be a delay in improvement of symptoms after improvement in signs are observed. Post-hoc analyses of SANSIKA support a lag time effect on symptoms: Spearman correlation coefficient between the change in CFS and OSDI overtime increased slightly from Month 1 to 6, even though it was not conclusive. Furthermore the pharmacologic and clinical profile of IKERVIS® suggests that it has the potential to provide consistent and efficacious anti-inflammatory effects, which may translate into a clinical benefit for the ocular surface.

In this context, the CHMP has recommended Santen to conduct a PAES (Post-Approval Efficacy Study) to further explore long term effects of IKERVIS® on signs, symptoms and ocular surface complications.

In order to establish IKERVIS® long-term efficacy and safety, the NVG14L127 trial proposes a 2-Period design: a one-year open label period (Period 1) to establish patient's response status according to the improvement on sign (ie. CFS); and Period 2 to assess, over 24 months, IKERVIS® long-term response in patients markedly improved after period 1, who will be randomised to receive either IKERVIS® or Vehicle, once daily.

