2. STUDY OBJECTIVES AND ENDPOINTS

2.1. Objectives

The primary objectives of this study are:

- To evaluate the long-term efficacy of a continuous treatment of IKERVIS® (1mg/mL ciclosporin) eye drops in adult dry eye disease (DED) subjects with severe keratitis on corneal sign and DED symptoms, and to estimate the lag time (if any) to improvement in symptoms (if any).
- To assess the ocular surface complications (defined as corneal ulceration, corneal perforation, loss of visual acuity, and ocular infection) over the three-year study period.

The secondary objectives of this study are:

- To evaluate the efficacy parameters (signs and symptoms), the ocular surface complications, and the quality of life over treatment Periods 1 and 2.
- For 12-month markedly improved subjects, to evaluate and compare signs and symptoms evolution in IKERVIS® group versus Vehicle group during the randomised period of the study (Period 2).
- To evaluate the safety and tolerability of IKERVIS® (1mg/mL ciclosporin) eye drops treatment over the three-year study period.

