8.1.1. Primary Analysis

For Period 1 analysis, Spearman correlation coefficient and its 95% confidence interval will be calculated for the correlation analysis between change from baseline in CFS score at visit X and SANDE symptoms score at each visit X+i in period 1 using the FAS Period 1 population.

The primary efficacy endpoint analysis result will be presented graphically by plotting Spearman correlation coefficients calculated at each visit. Spearman correlation coefficients will be plotted for the timepoints where more than 2 lagtime correlations are calculated. The plots will have x-axis to show lags, i, and y-axis to show Spearman correlation coefficients as shown in Figure 2, which is for X = Month 3.

Figure 2. A Sample Plot of Correlation between Change from Baseline in CFS Score at Visit X vs. Change from Baseline in SANDE Score at Visit X + i

Spearman Correlation Coefficients Calculated at Month 3

Interpretation of the results from graphical analysis:

- o If any individual graph shows a "bump" or a plateau at any lag > 0 point, as shown in Figure 2, it would be considered as an indication of existence of a lagged symptom response for CFS score at that particular visit X.
- o If there are at least half (50%) of the graphs show lagged symptom responses, we would conclude that dry eye symptoms (measured by SANDE questionnaire) show lagged response improvement in comparison to dry eye sign improvement.

For Period 2 analysis, Spearman correlation coefficient between change from baseline in CFS score at visit X and SANDE symptoms score at each visit X+i, its 95% confidence interval will be calculated by treatment group. The analysis will be based on the FAS Period 2 population.

For long term efficacy, the Entire Study analysis will be performed by repeating the Period 1 analysis for the entire 3 year duration using the FAS Entire Study population.

The analysis details are shown in Table 4 by study period.

Table 4 Analysis of Correlation between Change from Reference Point in CFS Score at Visit X and Change from Reference Point in SANDE Symptom Score at Visit X + i

Study Period / Analysis Population	Reference Point	Visit X	Visit X + i
Period 1 FAS Period 1 subjects	Baseline	Month 3*	Month 3, Month 6, Month 9, Month 12
		Month 6*	Month 6, Month 9, Month 12
		Month 9	Month 9, Month 12
		Month 12	Month 12

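### The lag rule in SAP 8.1.1 can declare symptom improvement from the shape of rank correlations alone, with no condition that SANDE improved

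*SAP*

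**What the plan says.** The first primary objective in SAP 2.1 has two parts. One is "To evaluate the long-term efficacy of a continuous treatment of IKERVIS" on corneal sign and symptoms. The other is the lag time to symptom improvement, where both the lag and the improvement are allowed to be absent.

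SAP 8.1 gives one primary efficacy endpoint: "The primary efficacy endpoint is the correlation between change from baseline in CFS score and SANDE symptoms score at each visit", together with the cross-correlation of sign at visit X with symptoms at visit X+i. In SAP 8.1.1, "Spearman correlation coefficient and its 95% confidence interval will be calculated" and plotted against the lag i. A bump or plateau at any lag above 0 counts as a lagged response for that visit X. If half or more of the plots show one, "we would conclude that dry eye symptoms (measured by SANDE questionnaire) show lagged response improvement in comparison to dry eye sign improvement". Table 4 marks two visits for plotting in Period 1 (Months 3 and 6), so one plot is enough there. The Entire Study analysis repeats the Period 1 analysis over three years and is described as serving long-term efficacy.

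Mean changes in CFS and SANDE are secondary (SAP 2.2.2). SAP 8.2.1 plans them as n, mean, SD, median, minimum and maximum. It adds an MMRM of change from Month 12 for Period 2, with 95% confidence intervals.

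**The concern.** Protocol 11.1 and 11.6 define improvement in CFS and in SANDE as a negative change. That is a statement about the level of change. A rank correlation describes whether patients with larger CFS changes also tend to have larger SANDE changes. It does not say in which direction, or how far, the group moved.

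The rule in SAP 8.1.1 moves from the second kind of statement to the first. The step fails even if the correlation curve were known without error, so this is separate from how a bump is recognised on a plot. The primary analysis could report a lagged symptom improvement when mean SANDE was flat or worse. It could also miss a late improvement shared equally by all patients. Symptoms are what the trial is meant to clarify: Protocol 4.2 says the earlier trials did not show a benefit over vehicle on them.

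**Working it through.** **The plan's own figure.** The documents give no precision or power for the correlation. The only efficacy figure is a mean CFS difference of 0.4 with SD 1.10, 147 versus 98 patients and 80% power (SAP 3.3). Assuming two-sided alpha 0.05, which is not stated: standard error = 1.10 × √(1/147 + 1/98) = 0.1434; 0.4/0.1434 = 2.79; 2.79 − 1.96 = 0.83; power = 79.6%. It reproduces, and it concerns means.

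**Shift property.** Let c be a patient's CFS change at visit X and s the SANDE change at visit X+i. Spearman's coefficient is the Pearson correlation of rank(c) and rank(s). For any constants a and b, rank(c + a) = rank(c) and rank(s + b) = rank(s). So r(c + a, s + b) = r(c, s), while the mean of s becomes mean(s) + b. The constant b may differ from visit to visit. The curve of r against lag can therefore keep its shape under any path of mean SANDE. A confidence interval built from r and n does not move either.

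**Numerical check.** One simulated set: N = 350 (planned enrolment), assumed latent correlation 0.3, CFS changes rounded to whole grades. Constants were then added to every patient's change.

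| Case | Mean CFS change | Mean SANDE change | Spearman r |
|---|---|---|---|
| Both improve | -1.91 | -18.4 | 0.248 |
| Both flat | +0.09 | +1.6 | 0.248 |
| Both worsen | +2.09 | +21.6 | 0.248 |
| CFS improves, SANDE worsens | -1.91 | +21.6 | 0.248 |

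The equality follows from the algebra; the table only shows what it means in practice.

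**Floor and ceiling.** CFS runs from 0 to 5 with entry at 3 or more, and SANDE from 0 to 100. The check was repeated with scores held inside those limits, assuming baseline CFS of 3, 4 and 5 in 50%, 35% and 15% of patients and a baseline SANDE of 60 for all.

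| Case | Mean CFS change | Mean SANDE change | Spearman r |
|---|---|---|---|
| Improve | -1.89 | -18.2 | 0.239 |
| Flat | -0.06 | +1.4 | 0.254 |
| Worsen | +0.66 | +19.8 | 0.221 |

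The values are no longer identical, but they do not separate improvement from worsening.

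**The rule itself.** In 1,500 simulated Period 1 trials (cross-correlation 0.3 at every lag, within-measure correlation 0.6), a bump was read as any later coefficient above the lag-0 one. The rule was met in 91.7% of trials whether means improved, stayed flat or worsened. The height of that figure depends on the assumptions: with flat means it was 55.5% or 24.6% when the cross-correlation fell by a factor of 0.9 or 0.8 per visit. Only its equality across the three mean patterns matters here.

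**Text check.** Neither SAP 8.1.1 nor Table 4 makes the conclusion depend on mean SANDE or mean CFS change. SAP 10.2 drops the word mean from the endpoint and does not touch the rule.

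**The case against.** Four points can be made for the plan.

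- **The means are already planned.** They are tabulated at every visit (SAP 8.2.1), stand beside the correlations in the interim analysis (SAP 10.3), and carry confidence intervals through the Period 2 MMRM. For Period 1 an interval follows from n, mean and SD. This stands: the information is not missing. But the rule does not refer to it.
- **The study is exploratory.** There are no hypotheses for primary or secondary endpoints (Protocol 13.1.2) and no multiplicity plan (SAP 5.4). This stands, and it limits the remedy. It does not justify a pre-specified conclusion that the statistic cannot carry.
- **Cross-correlation suits the lag question.** It does, for the timing of association, and it should be kept for that.
- **Shift invariance is not exact on bounded scales.** True, as the second table shows.

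Two stronger readings are tempting. A reader might infer that the primary endpoint must be replaced by mean change because the trial cannot otherwise address efficacy. The documents do not support that. With no primary hypotheses, promoting means that are already reported would be largely relabelling. Uncontrolled change from Day 1 would also not isolate a drug effect, and patients treated for three years are selected as Month 12 responders.

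A reader might also take the sponsor's pivotal trial as proof of the failure, since the "Spearman correlation coefficient between the change in CFS and OSDI overtime increased slightly from Month 1 to 6". Protocol 4.2 itself calls that result inconclusive. Protocol 4.1.1 reports: "The mean change from baseline in the 100-point OSDI score was -13.6 with IKERVIS® and -14.1 with vehicle at Month 6". Symptoms fell in both arms. What was absent was a difference from vehicle: -13.6 − (-14.1) = +0.5, p = 0.858. That example does not show a rising correlation without symptom improvement.

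**Conclusion.** The point holds for the decision rule. The planned conclusion of a lagged improvement rests on the shape of Spearman coefficients, which are unaffected by a common shift in all patients' changes and nearly so in the one bounded-scale example tried. As written, the rule can give that conclusion when mean SANDE is flat or worse.

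The shift property needs no assumption about the data beyond the absence of floor and ceiling effects. The simulated values rest on the assumptions listed with them. How often the rule would mislead in this trial cannot be derived from the documents. Data collection and the secondary analyses are unaffected, so this is a correction that should be made to the SAP, not a defect of the design.

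**What to change.** 1. In SAP 8.1.1, allow the words lagged response improvement only if mean SANDE change at the lagged visit X+i has a 95% confidence interval wholly below 0 and is more negative than at visit X. Use the correlation's own reference point from Table 4: Day 1 for Period 1 and Entire Study, Month 12 for Period 2, by treatment arm. Otherwise report only a change in correlation.
2. In SAP 8.2.1, add 95% confidence intervals to the mean CFS and SANDE changes from Day 1, and present them beside the correlations.
3. Show Entire Study results separately for patients randomised to IKERVIS. FAS Entire Study in SAP 6 includes all randomised patients, so vehicle patients are in it, whereas the objective concerns "To evaluate the long-term efficacy of a continuous treatment of IKERVIS® (1mg/mL ciclosporin) eye drops".
4. State that a within-group interval below 0 shows improvement from the reference point, not a drug effect. The Period 2 MMRM difference addresses the drug effect.

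The cost is SAP wording and a few added intervals. The bump rule is not in the protocol, so the protocol endpoint stays as it is. The downside is that the lag conclusion becomes harder to reach, perhaps most in Period 2, where patients start from a Month 12 state already selected for marked CFS improvement. The comparison with visit X is between point estimates and should be described as such.
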